### 11.1.6. Management of missing data

#### Demography:

- For a given subject and a given demographic variable, missing measurements will not be replaced.

#### Immunogenicity:

- For a given subject and a given immunogenicity measurement time point, missing or non-evaluable measurements will not be replaced.

#### Reactogenicity and safety:

- Subjects who missed reporting symptoms (solicited/unsolicited or concomitant medications) will be treated as subjects without symptoms (solicited/unsolicited or concomitant medications, respectively).

### 11.1.7. Data presentation description

The following decimal description from the decision rules will be used for the demography, immunogenicity and safety/reactogenicity.

Display Table	Parameters	Number of decimal digits
All summaries	% of count, including LL & UL of CI	1
Demographic characteristics	Mean, median, SD	1
Immunogenicity	% of difference, including LL & UL of CI	2
Immunogenicity	GMC group ratio, including LL & UL of CI	2
Immunogenicity	Anti-RV IgA GMC	1

## 12. ANNEX 2: SUMMARY ON ELIMINATION CODES

Refer to Section [5.2](#).

**13. ANNEX 3: STUDY SPECIFIC MOCK TFL**

The following draft study specific mock TFLs will be used.

The data display, title and footnote are for illustration purpose and will be adapted to the study specificity as indicated in the TFL TOC.

These templates were copied from ROTA-061 and additional tables required for public disclosure were added. Note that there may be few changes between the study specific SAP mock TFL and the final TFLs. These editorial/minor changes will not lead to a SAP amendment.

Note that all tables will include the pooled lot group for HRV liquid as shown in [Template 2](#).

**Template 1 Minimum and maximum activity dates (Exposed Set)**

Visit	Minimum date	Maximum date
1	19JUN2007	29DEC2007
2	24JUL2007	08FEB2008
3	24AUG2007	18MAR2008
4	25MAR2008	22NOV2008
5	24MAR2009	31MAR2009*

\*Database Lock Date = 31MAR2009

**Template 2 Number of subjects enrolled by center - Exposed Set**

Country	Center	LIQ_A	LIQ_B	LIQ_C	LIQ_pool	LYO	Total	
		n	n	n	n	n	n	%
XXXX	PPD	38	38	38		37	151	12.6
	PPD	20	20	20		20	80	6.7
	PPD	30	30	29		29	118	9.8
	PPD	19	19	20		20	78	6.5
	All							
YYYYY	PPD	15	15	15		15	60	5.0
	PPD	22	22	23		22	89	7.4
	PPD	35	36	36		35	142	11.8
	PPD	28	28	28		28	112	9.3
	PPD	20	21	20		21	82	6.8
	PPD	22	23	22		23	90	7.5
	PPD	22	23	22		23	90	7.5
	PPD	27	27	27		27	108	9.0
	All							
All	All	298	302	300		300	1200	100

<group description >

n = number of subjects included in each group or in total for a given center or for all centers

All = sum of all subjects in each group or in total (sum of all groups)

% = n/All x 100

**Template 3 Number of subjects vaccinated, completed and withdrawn with reason for withdrawal entire study period- Exposed Set**

	LIQ_A	LIQ_B	LIQ_C	LYO	Total
Number of subjects vaccinated	298	302	300	300	1200
Number of subjects completed	297	301	298	297	1193
Number of subjects withdrawn	1	1	2	3	7
Reasons for withdrawal :					
Serious Adverse Event	0	0	0	1	1
Non-serious adverse event	0	0	0	0	0
Protocol violation	0	0	0	0	0
Consent withdrawal (not due to an adverse event)	1	0	1	2	4
Migrated/moved from study area	0	1	1	0	2
Lost to follow-up (subjects with incomplete vaccination course)	0	0	0	0	0
Lost to follow-up (subjects with complete vaccination course)	0	0	0	0	0
Others	0	0	0	0	0

LIQ\_A = HRV vaccine liquid formulation Lot A

LIQ\_B = HRV vaccine liquid formulation Lot B

LIQ\_C = HRV vaccine liquid formulation Lot C

LYO = HRV vaccine lyophilised formulation

Vaccinated = number of subjects who were vaccinated in the study

Completed = number of subjects who completed study visit 3

Withdrawn = number of subjects who did not come for study visit 3

Essential serological data missing (code 2100)		87	95			23	25		21	22		20	22		23	26
Subjects with incomplete study vaccination schedule but with post serological result (code 2500)		1	1			0	0		1	1		0	0		0	0
Per protocol set	998			83.2	242			260			244			252		

LIQ\_A = HRV vaccine liquid formulation Lot A    LIQ\_B = HRV vaccine liquid formulation Lot B

LIQ\_C = HRV vaccine liquid formulation Lot C    LYO = HRV vaccine lyophilised formulation

Note: Subjects may have more than one elimination code assigned

n = number of subjects with the elimination code assigned excluding subjects who have been assigned a lower elimination code number

s = number of subjects with the elimination code assigned

% = percentage of subjects in the per protocol set (PPS) relative to the exposed set (ES)

**Template 6 Summary of demographic characteristics (Per Protocol Analysis Set of Immunogenicity)**

Characteristics	Parameters or Categories	LIQ_A N = 242		LIQ_B N = 260		LIQ_C N = 244		LYO N = 252		Total N = 998	
		Value or n	%	Value or n	%	Value or n	%	Value or n	%	Value or n	%
Age at Dose 1 of HRV vaccine (weeks)	Mean	11.6	-	11.5	-	11.5	-	11.6	-	11.6	-
	SD	1.32	-	1.16	-	1.19	-	1.20	-	1.22	-
	Median	11.0	-	11.0	-	11.0	-	11.0	-	11.0	-
	Minimum	10	-	10	-	10	-	10	-	10	-
	Maximum	17	-	15	-	15	-	16	-	17	-
Age at Dose 2 of HRV vaccine (weeks)	Mean	16.6	-	16.5	-	16.5	-	16.7	-	16.6	-
	SD	1.48	-	1.40	-	1.37	-	1.34	-	1.40	-
	Median	17.0	-	16.0	-	16.0	-	17.0	-	17.0	-
	Minimum	14	-	14	-	14	-	14	-	14	-
	Maximum	22	-	20	-	20	-	21	-	22	-
Gender	Female	122	50.4	121	46.5	120	49.2	120	47.6	483	48.4
	Male	120	49.6	139	53.5	124	50.8	132	52.4	515	51.6
Ethnicity	American Hispanic or Latino	0	0.0	2	0.8	1	0.4	0	0.0	3	0.3
	Not American Hispanic or Latino	242	100.0	258	99.2	243	99.6	252	100.0	995	99.7
Race	African heritage / African American	1	0.4	0	0.0	1	0.4	0	0.0	2	0.2
	American Indian or Alaskan native	0	0.0	0	0.0	0	0.0	0	0.0	0	0.0
	Asian - central/south Asian heritage	0	0.0	0	0.0	0	0.0	0	0.0	0	0.0
	Asian - east Asian heritage	0	0.0	0	0.0	0	0.0	0	0.0	0	0.0
	Asian - Japanese heritage	0	0.0	0	0.0	0	0.0	0	0.0	0	0.0
	Asian - south east Asian heritage	0	0.0	0	0.0	0	0.0	0	0.0	0	0.0
	Native Hawaiian or other pacific islander	0	0.0	0	0.0	0	0.0	0	0.0	0	0.0
	White - Arabic / north African heritage	0	0.0	0	0.0	2	0.8	0	0.0	2	0.2
	White - Caucasian / European heritage	239	98.8	258	99.2	240	98.4	247	98.0	984	98.6
	Other	2	0.8	2	0.8	1	0.4	5	2.0	10	1.0
Height at Visit 1 (cm)	Mean	60.4	-	60.5	-	60.7	-	60.6	-	60.5	-
	SD	2.35	-	2.37	-	2.32	-	2.22	-	2.32	-
	Median	61.0	-	60.0	-	61.0	-	61.0	-	61.0	-
	Unknown	0	-	1	-	2	-	0	-	3	-
Weight at Visit 1 (kg)	Mean	6.0	-	6.1	-	6.2	-	6.1	-	6.1	-
	SD	0.77	-	0.76	-	0.77	-	0.75	-	0.76	-
	Median	6.0	-	6.0	-	6.2	-	6.1	-	6.1	-
BMI at Visit 1 (kg/m  )	Mean	16.5	-	16.6	-	16.7	-	16.7	-	16.6	-
	SD	1.49	-	1.46	-	1.46	-	1.46	-	1.47	-
	Median	16.3	-	16.5	-	16.5	-	16.7	-	16.5	-
	Unknown	0	-	1	-	2	-	0	-	3	-

LIQ\_A = HRV vaccine liquid formulation Lot A  
 LIQ\_B = HRV vaccine liquid formulation Lot B  
 LIQ\_C = HRV vaccine liquid formulation Lot C

LYO = HRV vaccine lyophilised formulation  
 N = total number of subjects  
 n (%) = number / percentage of subjects in a given category  
 Value = value of the considered parameter  
 SD = standard deviation

**Template 7 Deviations from specifications for age and intervals between study visits - Exposed Set**

Group		Age	PRE-Dose:1	Dose:1-Dose:2		Dose:2-P11(M2)	
		Protocol	Protocol	Protocol	Adapted	Protocol	Adapted
		from 10 to 17 weeks	from 0 to 0 days	from 30 to 48 days	from 21 to 48 days	from 30 to 48 days	from 21 to 48 days
LIQ_A	N	298	298	297	297	287	287
	n	0	2	8	7	1	1
	%	0.0	0.7	2.7	2.4	0.3	0.3
	range	10 to 17	0 to 4	29 to 76	29 to 76	30 to 55	30 to 55
LIQ_B	N	302	302	301	301	294	294
	n	0	1	0	0	4	2
	%	0.0	0.3	0.0	0.0	1.4	0.7
	range	10 to 15	0 to 3	30 to 48	30 to 48	24 to 56	24 to 56
LIQ_C	N	300	300	300	300	291	291
	n	1	1	8	7	4	4
	%	0.3	0.3	2.7	2.3	1.4	1.4
	range	9 to 17	0 to 9	27 to 76	27 to 76	30 to 56	30 to 56
LYO	N	300	300	299	299	289	289
	n	0	2	4	4	5	3
	%	0.0	0.7	1.3	1.3	1.7	1.0
	range	10 to 16	0 to 3	30 to 61	30 to 61	28 to 61	28 to 61

LIQ\_A = HRV vaccine liquid formulation Lot A  
 LIQ\_B = HRV vaccine liquid formulation Lot B  
 LIQ\_C = HRV vaccine liquid formulation Lot C  
 LYO = HRV vaccine lyophilised formulation  
 PRE = pre-vaccination  
 P11 (M2) = blood sample taken one month after Dose 2 of the HRV vaccine (Visit 3)  
 Adapted = interval used for defining the ATP cohorts for immunogenicity  
 N = total number of subjects with available results  
 n/% = number / percentage of subjects with results outside of the interval  
 range = minimum-maximum for age and intervals

**Template 8 Summary of co-administered vaccination by dose - Exposed Set**

Dose1	LIQ_A N = 298		LIQ_B N = 302		LIQ_C N = 300		LYO N = 300		Total N = 1200	
Characteristics	Value or n	%	Value or n	%	Value or n	%	Value or n	%	Value or n	%
Any	298	100	302	100	299	99.7	300	100	1199	99.9
Infanrix hexa	298	100	302	100	299	99.7	300	100	1199	99.9
Dose 2	LIQ_A N = 297		LIQ_B N = 301		LIQ_C N = 300		LYO N = 299		Total N = 1197	
Characteristics	Value or n	%	Value or n	%	Value or n	%	Value or n	%	Value or n	%
Any	297	100	301	100	298	99.3	299	100	1195	99.8
Infanrix hexa	297	100	301	100	298	99.3	299	100	1195	99.8

LIQ\_A = HRV vaccine liquid formulation Lot A

LIQ\_B = HRV vaccine liquid formulation Lot B

LIQ\_C = HRV vaccine liquid formulation Lot C

LYO = HRV vaccine lyophilised formulation

N = total number of subjects having received the considered dose of HRV

n/% = number/percentage of subjects who received the specified vaccination on the same day as the considered dose of HRV vaccine

**Template 9 Summary of vaccinations other than HRV vaccine administered from birth until Visit 3, excluding vaccination given on the day of HRV doses - Exposed Set**

Before Dose 1	LIQ_A N = 298			LIQ_B N = 302			LIQ_C N = 300			LYO N = 300			Total N = 1200		
Characteristics	#	n	%	#	n	%	#	n	%	#	n	%	#	n	%
Any	18	18	6.0	11	11	3.6	13	13	4.3	25	25	8.3	67	67	5.6
BCG	18	18	6.0	11	11	3.6	12	12	4.0	25	25	8.3	66	66	5.5
Infanrix hexa TM	0	0	0.0	0	0	0.0	1	1	0.3	0	0	0.0	1	1	0.1
Between Dose 1 and Dose 2§	LIQ_A N = 298			LIQ_B N = 302			LIQ_C N = 300			LYO N = 300			Total N = 1200		
Characteristics	#	n	%	#	n	%	#	n	%	#	n	%	#	n	%
Any	0	0	0.0	2	1	0.3	0	0	0.0	0	0	0.0	2	1	0.1
Infanrix hexa TM	0	0	0.0	2	1	0.3	0	0	0.0	0	0	0.0	2	1	0.1
Between Dose 2 and Visit 3*	LIQ_A N = 297			LIQ_B N = 301			LIQ_C N = 300			LYO N = 299			Total N = 1197		
Characteristics	#	n	%	#	n	%	#	n	%	#	n	%	#	n	%
Any	291	291	98.0	295	295	98.0	287	286	95.3	290	290	97.0	1163	1162	97.1
DTPa+IPV+Hib	0	0	0.0	1	1	0.3	0	0	0.0	0	0	0.0	1	1	0.1
Infanrix hexa TM	291	291	98.0	294	294	97.7	287	286	95.3	290	290	97.0	1162	1161	97.0

LIQ\_A = HRV vaccine liquid formulation Lot A

LIQ\_B = HRV vaccine liquid formulation Lot B

LIQ\_C = HRV vaccine liquid formulation Lot C

LYO = HRV vaccine lyophilised formulation

N = Before Dose 1 and between Dose 1 and Dose 2: total number of subjects having received dose 1 of HRV

Between Dose 2 and visit 3: total number of subjects having received dose 2 of HRV

#= number of doses administered of the specified vaccination excluding vaccination given on the day of HRV doses

n/% = number/percentage of subjects who received at least one specified vaccination between the considered visits excluding vaccination given on the day of HRV doses

§= up to last contact of conclusion at Visit 3 if dose 2 of HRV was not administered

\*= up to last contact of conclusion at Visit 3 if visit 3 was not done

**Template 10 Anti-rotavirus IgA antibody GMC and seroconversion rates – Per Protocol Analysis Set of Immunogenicity**

			≥ 20 U/ml				GMC (U/ml)		
					95% CI				
Group	Timing	N	n	%	LL	UL	value	LL	UL
LIQ_A	PRE	242	0	0.0	0.0	1.5	<20	-	-
	PII(M2)	242	220	90.9	86.6	94.2	384.4	309.1	478.2
LIQ_B	PRE	260	0	0.0	0.0	1.4	<20	-	-
	PII(M2)	260	235	90.4	86.1	93.7	418.8	337.8	519.1
LIQ_C	PRE	244	0	0.0	0.0	1.5	<20	-	-
	PII(M2)	244	206	84.4	79.3	88.7	324.4	253.4	415.3
LIQPOOL	PRE	746	0	0.0	0.0	0.5	<20	-	-
	PII(M2)	746	661	88.6	86.1	90.8	374.7	328.8	426.9
LYO	PRE	252	0	0.0	0.0	1.5	<20	-	-
	PII(M2)	252	228	90.5	86.2	93.8	331.8	265.0	415.4

LIQ\_A = HRV vaccine liquid formulation Lot A      LIQ\_B = HRV vaccine liquid formulation Lot B  
 LIQ\_C = HRV vaccine liquid formulation Lot C      LIQPOOL = Pooled HRV vaccine liquid formulation  
 LYO = HRV vaccine lyophilised formulation  
 N = number of subjects with available results  
 n (%) = number/percentage of subjects with concentration above the cut-off  
 95% CI = 95% Confidence Interval; L.L = Lower limit; U.L = upper limit  
 Pre = pre-vaccination  
 PII (M2) = blood sample taken one month after Dose 2 of HRV vaccine (Visit 3)

**Template 11 Anti-rotavirus IgA antibody GMC calculated on subjects seropositive for anti-rotavirus IgA antibodies – Per Protocol Analysis Set of Immunogenicity**

			GMC		
			95% CI		
Group	Timing	N	value	LL	UL
LIQ_A	PII(M2)	220	553.8	463.4	661.7
LIQ_B	PII(M2)	235	623.0	525.0	739.4
LIQ_C	PII(M2)	206	616.4	510.4	744.4
LIQPOOL	PII(M2)	661	597.1	538.7	661.8
LYO	PII(M2)	228	479.7	395.4	582.0

LIQ\_A = HRV vaccine liquid formulation Lot A      LIQ\_B = HRV vaccine liquid formulation Lot B  
 LIQ\_C = HRV vaccine liquid formulation Lot C      LIQPOOL = Pooled HRV vaccine liquid formulation  
 LYO = HRV vaccine lyophilised formulation  
 N = number of subjects who were seropositive for anti-rotavirus IgA antibodies  
 95% CI = 95% Confidence Interval; LL = Lower Limit; UL = Upper Limit  
 PII(M2) = blood sample taken one month after Dose 2 of HRV vaccine (Visit 3)

**Template 12 Ratio of anti-rotavirus IgA antibody GMCs 1-2 months after Dose 2 of the HRV vaccine between each pair of the three lots of the HRV PCV-free liquid vaccine – Per Protocol Analysis Set of Immunogenicity**

						GMC ratio			
								95% CI	
Group	N	GMC	Group	N	GMC	Ratio order	Value	LL	UL
LIQ_A	242	384.4	LIQ_B	260	418.8	LIQ_A /LIQ_B	0.92	0.67*	1.26*
LIQ_A	242	384.4	LIQ_C	244	324.4	LIQ_A /LIQ_C	1.19	0.86*	1.64*
LIQ_B	260	418.8	LIQ_C	244	324.4	LIQ_B /LIQ_C	1.29	0.94*	1.77*

LIQ\_A = HRV vaccine liquid formulation Lot A      LIQ\_B = HRV vaccine liquid formulation Lot B

LIQ\_C = HRV vaccine liquid formulation Lot C

N = number of subjects with available results

95% CI = 95% Confidence Interval (one-way ANOVA model with pooled variance from the four groups)

L.L. = Lower Limit, U.L. = Upper Limit

\*The two-sided 95% CIs are within [0.5; 2] (the pre-defined clinical limit interval for consistency)

**Template 13 Difference between groups in the percentage of subjects who seroconverted for anti-rotavirus IgA antibody 1-2 months after Dose 2 of the HRV vaccine – Per Protocol Analysis Set of Immunogenicity**

						Difference in seroconversion rate			
								95 % CI	
Group	N	%	Group	N	%	Difference	%	LL	UL
LIQPOOL	746	88.6	LYO	252	90.5	LYO - LIQPOOL	1.87	-2.85	5.83*

LIQPOOL = Pooled HRV vaccine liquid formulation

LYO = HRV vaccine lyophilised formulation

N = number of subjects with available results

% = percentage of subjects who seroconverted at visit 3

95% CI = asymptotic standardised 95% Confidence Interval; LL = Lower Limit; UL = Upper Limit

\*Lower limit of the 95% CI  $\geq$  -10% (the pre-defined clinical limit for non-inferiority)

**Template 14 Ratio of anti-rotavirus IgA antibody GMCs 1-2 months after Dose 2 of the HRV vaccine between the HRV lyophilised vaccine group and the pooled HRV PCV-free liquid vaccine – Per Protocol Analysis Set of Immunogenicity**

						GMC ratio			
								95% CI	
Group	N	GMC	Group	N	GMC	Ratio order	Value	LL	UL
LIQPOOL	746	373.8†	LYO	252	331.8	LYO /LIQPOOL	0.89	0.68	1.15*

LIQPOOL = Pooled HRV vaccine liquid formulation

LYO = HRV vaccine lyophilised formulation

N = number of subjects with available results

[figure not shown]
†geometric mean of the 3 GMC from the HRV liquid formulation groups

95% CI = 95% Confidence Interval (one-way ANOVA model using the group contrast between the HRV lyophilised formulation group and average of the HRV liquid formulation groups)

L.L. = Lower Limit, U.L. = Upper Limit

\*Lower limit of the 95% CI  $\geq$  0.67 (the pre-defined clinical limit for non-inferiority)

**Template 15 Reverse cumulative distribution curve for anti-rotavirus IgA antibody concentrations at Visit 3 - Per Protocol Analysis Set of Immunogenicity**

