### 10.3.3. Power computation

The power computations were based on the following methods

- Consistency on GMC: Type II error was obtained using Power Analysis and Sample Size (PASS) 2005, one-sided non-inferiority test for 2 means, under the alternative of equal means & alpha=2.5%. The type II error was multiplied by 6 to account for the 6 pair wise lot comparisons.
- NI on Seroconversion rate: Type II error was obtained using PASS 2005, one-sided non-inferiority test for 2 proportions, under the alternative of equal proportions (Miettinen and Nurminen’s Likelihood Score Test of the Difference).
- NI on GMC: Type II error was obtained using PASS 2005, one-sided non-inferiority test for 2 means, under the alternative of equal means and variances.

To account for the multiplicity of comparison, the global type II errors were conservatively estimated as the sum of individual type II errors.

**Table 17 Power to demonstrate that the two-sided 95% CIs on the anti-RV IgA GMC ratio between PCV free liquid vaccine, 1-2 months after dose 2 of HRV vaccine lots are within the [0.5; 2.0] interval for all the pair wise comparisons**

Endpoint	Standard deviation [Log 10 (titre)]	N evaluable (each PCV free HRV liquid group)	Power
Anti-RV IgA antibody concentration	0.750	320	99.4%
	0.790*	320	98.2%
	0.850	320	96.4%

\*=Reference used for the global power computation

**Table 18 Probability that the lower limit of 95% CI for the difference in seroconversion rate (the pooled PCV free liquid vaccine group minus the lyophilised vaccine group), 1-2 months after dose 2 of HRV vaccine is ≥-10%**

Seroconversion rate		N evaluable (pooled PCV free HRV liquid group)	N evaluable (lyophilised HRV group)	Power
Lyophilised formulation of HRV vaccine	Liquid formulation of PCV free HRV vaccine			
75%	75%	960	320	96.0%
80%	80%	960	320	98.1%
85%*	85%*	960	320	99.5%
90%	90%	960	320	99.9%

\*=Reference used for the global power computation

**Table 19 Probability that the lower limit of the 95% CI on anti-rotavirus IgA antibody GMC ratio (the pooled PCV free liquid vaccine group divided by the lyophilised vaccine group), 1-2 months after dose 2 of HRV vaccine is  $\geq 0.67$**

Endpoint	Standard deviation [Log 10 (titre)]	N evaluable (pooled PCV free HRV liquid group)	N evaluable (lyophilised HRV group)	Power
Anti-RV IgA antibody concentration	0.750	960	320	95.3%
	0.790*	960	320	93.2%

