### 3. OBJECTIVES

#### 3.1. Co-Primary

- To demonstrate the lot-to-lot consistency of the PCV-free liquid HRV vaccine in terms of immunogenicity as measured by serum anti-RV IgA antibody concentrations 1-2 months after Dose 2.

*Consistency will be demonstrated if, for all pairs of lots, the two-sided 95% confidence intervals (CIs) for the ratio of anti-RV IgA antibody GMCs 1-2 months after Dose 2 are within the [0.5; 2] clinical limit interval.*

- To demonstrate the immunological non-inferiority of PCV-free liquid HRV vaccine as compared to the currently licensed lyophilised HRV vaccine in terms of seroconversion rates 1-2 months after Dose 2.

*Non-inferiority will be demonstrated if the lower limit of the two-sided asymptotic standardized 95% CI for the difference in seroconversion rate between the PCV-free liquid HRV vaccine (pooled HRV liquid groups) and licensed lyophilised HRV vaccine is greater than or equal to -10%.*

- To demonstrate the non-inferiority of the PCV-free liquid HRV vaccine to that of the currently licensed lyophilised HRV vaccine in terms of serum anti-RV IgA antibody concentrations 1-2 months after Dose 2.

*Non-inferiority will be demonstrated if the lower limit of the two-sided 95% CI for the ratio of anti-RV IgA antibody GMCs 1-2 months after Dose 2 between the PCV-free liquid HRV vaccine (pooled HRV liquid groups) and the lyophilised HRV vaccine is greater than or equal to 0.67.*

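### Do the mock tables for the non-inferiority objectives (SAP Annex 3, Templates 13 and 14) flag success on the wrong limit?

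*SAP*

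**What the plan says.** SAP Section 3.1 sets both non-inferiority criteria on the liquid vaccine relative to the lyophilised one. The seroconversion criterion is a lower limit of at least -10% "for the difference in seroconversion rate between the PCV-free liquid HRV vaccine (pooled HRV liquid groups) and licensed lyophilised HRV vaccine". The GMC criterion is a lower limit of the ratio "between the PCV-free liquid HRV vaccine (pooled HRV liquid groups) and the lyophilised HRV vaccine is greater than or equal to 0.67". Section 10.3.3 of the protocol leaves no doubt about the order: Table 18 describes the difference as "the pooled PCV free liquid vaccine group minus the lyophilised vaccine group" and Table 19 describes the ratio as "the pooled PCV free liquid vaccine group divided by the lyophilised vaccine group".

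The shells in Annex 3 print the reverse. Template 13 shows LYO - LIQPOOL as 1.87 (-2.85 to 5.83), and Template 14 shows LYO /LIQPOOL as 0.89 (0.68 to 1.15). In both, the asterisk is on the upper limit. The footnotes explain it as a lower limit at or above minus "10% (the pre-defined clinical limit for non-inferiority", or at or above "0.67 (the pre-defined clinical limit for non-inferiority".

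On the model, Section 6.3.1.3 asks for vaccine group and country as fixed effects, and Section 6.3.2 restricts the lot comparison to the three liquid groups. The footnotes of Templates 12 and 14 describe a one-way ANOVA, and Template 12 takes its variance from all four groups.

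Annex 3 opens by stating the status of the shells: "These templates were copied from ROTA-061", and "The data display, title and footnote are for illustration purpose and will be adapted to the study specificity as indicated in the TFL TOC". It adds that editorial or minor differences in the final tables will not need a SAP amendment.

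**The concern.** Templates 13 and 14 carry the success flag for two of the three co-primary objectives. In each, the row label, the asterisk and the footnote cannot all be right. If the footnote were programmed on the contrast as printed, the flag would ask whether the lyophilised vaccine is non-inferior to the liquid one, which is the opposite of the objective. A liquid vaccine that was clearly worse could then be marked as having met the criterion, and a clearly better one could miss its mark. The mock figures pass in both directions, so checking output against the shell would not expose the slip. The one-way ANOVA footnotes raise a smaller worry of the same kind, that the country term might be left out of the programmed model.

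**Working it through.** **1. Are the printed numbers really lyophilised-first?**

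Template 13. Inputs from Template 10: lyophilised 228/252, pooled liquid 661/746. Method from SAP Section 11.1: the standardised asymptotic (score) interval, method six. The limits are the values d at which (p1 - p2 - d)/SE(d) = ±1.96, with SE(d) computed from the proportions fitted under a difference of d.

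- Lyophilised minus liquid: 1.87 (-2.85 to 5.83), which is the printed line.
- Liquid minus lyophilised, same data: -1.87 (-5.83 to 2.85).

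Template 14. Inputs from Template 10: GMCs of 384.4, 418.8 and 324.4 for the lots (n = 242, 260, 244) and 331.8 for lyophilised (n = 252). Log10 SDs back-calculated from the printed GMC intervals pool to 0.788 over the four groups.

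- Unweighted geometric mean of the three lots: 373.8, as printed.
- SE = 0.788 × sqrt(1/252 + (1/242 + 1/260 + 1/244)/9) = 0.0574 on log10.
- Lyophilised over liquid: 0.888 (0.685 to 1.151), matching the printed 0.89 (0.68 to 1.15).
- Liquid over lyophilised: 1.13 (0.87 to 1.46).

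So the shells do hold lyophilised-first results, computed without country.

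**2. Which pieces of each shell agree?**

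| Piece | Direction it belongs to |
|---|---|
| Row label and numbers | Lyophilised first |
| Asterisk on the upper limit | Lyophilised first |
| Footnote: lower limit ≥ -10%, ≥ 0.67 | Liquid first (Section 3.1) |

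For a lyophilised-first contrast, the Section 3.1 criteria become upper limit ≤ 10% and upper limit ≤ 1/0.67 = 1.49. The asterisks sit on the limits to which those tests apply, and both are met (5.83 and 1.15). The thresholds in the footnotes are those of Section 3.1. Each piece is sound in its own direction; the fault is that they are combined.

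**3. Does it matter on the mock data?**

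- Seroconversion: -2.85 (printed contrast) and -5.83 (Section 3.1 contrast) are both above -10.
- GMC: 0.68 and 0.87 are both above 0.67.

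The conclusion is the same either way.

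**4. What would a literal misreading do at the planned 960 against 320?**

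Illustrative counts: lyophilised 290/320 = 90.6%, liquid 768/960 = 80.0%.

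- Lyophilised minus liquid: 10.6 (6.3 to 14.5). The footnote rule on this contrast would be met.
- Liquid minus lyophilised: -10.6 (-14.5 to -6.3). Section 3.1 fails.

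GMC at the reference SD of 0.79 from Protocol Table 19: SE = 0.79 × sqrt(1/960 + 1/320) = 0.0510 on log10.

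- Section 3.1 needs an observed liquid/lyophilised ratio of at least 0.67 × 10^(1.96 × 0.0510) = 0.843.
- The footnote rule on the reversed ratio is met for any liquid/lyophilised ratio up to 1/0.843 = 1.186.

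A literal misreading would therefore be serious. It is also easy to see, because the same table would print 90.6%, 80.0% and an interval of 6.3 to 14.5 in favour of lyophilised.

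**5. The model footnotes.**

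Recomputing Template 12 with the three-group SD (0.7885) in place of the four-group SD (0.7881) moves no limit by more than 0.001. The effect of country cannot be computed from the documents.

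**The case for a change.** The strongest case for a correction is that these shells look half adapted. Their titles already name the PCV-free vaccine and the 1-2 month time point, and their footnotes state the margins this study uses. The same text appears in the first SAP and again in Amendment 1, whose history records only the gastroenteritis derivation. The TFL table of contents, which is meant to direct the adaptation, is not among the documents, so nobody can confirm that it repairs these tables. The direction of a co-primary flag is worth settling before unblinding, and the correction would take a few words.

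The inconsistency itself stands, and so does the point about the unseen TFL table of contents. The step to a likely programming error does not. Annex 3 cannot be used literally. Templates 13 and 14 hold the earlier study's sample sizes (746 and 252, as in Protocol Table 16), Template 1 has dates from 2007 to 2009, Template 7 uses other age and visit windows, and Template 33 lists meningococcal and HPV vaccine groups. Anyone programming from it has to return to the SAP text for the contrast, the margin and the model, and that text is correct. Nor do the documents show whether the margins in the footnotes were inserted for this study or came over with the shells.

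**Conclusion.** This is a clerical slip in illustrative tables, and no change to the plan follows. The success criteria are defined correctly in SAP Section 3.1, their direction is confirmed by Protocol Tables 18 and 19, and the model is fixed in SAP Sections 6.3.1.3 and 6.3.2. Following that text gives the intended decision, with type I error control and power untouched. Annex 3 already provides for adapting display, title and footnote without an amendment, and putting each table into one direction is that kind of adaptation. When it is done, Template 14's title and contrast footnote, which are also lyophilised-first, need the same direction as its row label.

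The model footnotes fall under the same reasoning. Template 14's note on averaging the three lots is the only text that says how they are combined for the ratio, but little depends on it. The unweighted mean is 373.8 and the mean weighted by group size is 374.7 (the pooled value in Template 10), so the mock ratio is 0.888 or 0.886.

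The conclusion assumes that the body of the SAP takes precedence over its illustrative annex, and that the final tables print both limits, as the shells do. On that basis the worst plausible result is a mislabelled asterisk beside numbers from which the right conclusion can still be read.
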